## **17.8 Use of Unused (Leftover) Specimens Collected for this Trial**

Unused samples in existence at study completion (i.e. completion of all research activities under this study) will either be: (a) placed in a COH IRB approved biorepository with some clinical information and potentially PHI attached or (b) discarded.

With regard to which option will apply, each site IRB may choose to either: (a) leave the determination to the participant via a question in the informed consent document, which would be communicated to the study registrar (DCC) at the time of participant registration, OR b) may choose to make a single determination on behalf of their respective participants, and communicate that determination to their respective participants via the informed consent.

### **17.9 Conflict of Interest**

Any investigator who has a conflict of interest with this study (patent ownership, royalties, or financial gain greater than the minimum allowable by their institution, etc.) must have the conflict reviewed by a properly constituted Conflict of Interest Committee with a Committee-sanctioned conflict management plan that has been reviewed and approved by the study Sponsor (City of Hope) prior to participation in this study. All City of Hope investigators will follow the City of Hope conflict of interest policy.

### **17.10 Financial Obligations, Compensation, and Reimbursement of Participants**

Venetoclax will be provided free of charge to participants.

Neither the research participant nor the insurance carrier will be responsible for the research procedures related to this study.

Standard of care drugs or procedures provided during the course of study participation will be the responsibility of the research participant and/or the insurance carrier. The participant will be responsible for all copayments, deductibles, and other costs of treatment and diagnostic procedures as set forth by the insurance carrier. The participant and/or the insurance carrier will be billed for the costs of treatment and diagnostic procedures in the same way as if the participant were not in a research study.

In the event of physical injury to a participant resulting from research procedures, appropriate medical treatment will be available at City of Hope or at the non-COH site to the injured participant. There are no plans for City of Hope to provide financial compensation in the event of physical injury to a participant.

The research participant will not receive reimbursement or payment for taking part in this study.

### **17.11 Publication/ Data Sharing**

Neither the complete nor any part of the results of the study carried out under this protocol, nor any of the information provided by City of Hope for the purposes of performing the study, will be published or passed on to any third party without the written approval of the Study PI. Any investigator involved with this study is obligated to provide City of Hope with complete test results and all data derived from the study.

The preparation and submittal for publication of manuscripts containing the study results shall be in accordance with a process determined by mutual written agreement between City of Hope and AbbVie. The publication or presentation of any study results shall comply with all applicable privacy laws, including, but not limited to, the Health Insurance Portability and Accountability Act of 1996.

In accordance with the [U.S. Public Law 110-85](#) (Food and Drug Administration Amendments Act of 2007 or FDAAA), Title VIII, Section 801, this trial will be registered onto [ClinicalTrials.gov](#) and results will be reported on [ClinicalTrials.gov](#) within 12 months of the estimated or actual completion date of the trial, whichever date is earlier.

**APPENDIX A: PERFORMANCE STATUS**

ECOG Performance Scale [54]	
Grade	Descriptions
0	Normal activity. Fully active, able to carry on all pre-disease performance without restriction.
1	Symptoms, but ambulatory. Restricted in physically strenuous activity, but ambulatory and able to carry out work of a light or sedentary nature (e.g., light housework, office work).
2	In bed <50% of the time. Ambulatory and capable of all self-care, but unable to carry out any work activities. Up and about more than 50% of waking hours.
3	In bed >50% of the time. Capable of only limited self-care, confined to bed or chair more than 50% of waking hours.
4	100% bedridden. Completely disabled. Cannot carry on any self-care. Totally confined to bed or chair.
5	Dead.

**APPENDIX B: TUMOR LYSIS SYNDROME CLASSIFICATION**

Based on Howard et al., 2011 [55].

Metabolic Abnormality	Criteria for Classification of Laboratory Tumor Lysis Syndrome*	Criteria for Classification of Clinical Tumor Lysis Syndrome**
Hyperuricemia	Uric acid > 8.0 mg/dl (475.8 $\mu$ mol/L)	
Hyperphosphatemia	Phosphorus > 4.5 mg/dl (1.5 mmol/L)	
Hyperkalemia	Potassium > 6.0 mmol/L	Cardiac dysrhythmia or sudden death probably or definitely caused by hyperkalemia
Hypocalcemia	Corrected calcium < 7.0 mg/dL (1.75 mmol/L or ionized calcium < 1.12 (0.3 mmol/L) †	Cardiac dysrhythmia, sudden death, seizure, neuromuscular irritability (tetany, paresthesias, muscle twitching, carpopedal spasm, Troussseau's sign, Chvostek's sign, laryngospasm, or bronchospasm), hypotension, or heart failure probably or definitely caused by hypocalcemia
Acute kidney injury ‡ If no institutional ULN is specified, age/sex ULN creatinine may be defined as follows: > 1 to < 12 years of age, both male and female, 61.6 <math>\mu</math>mol/L; ≥ 12 to < 16 years, both male and female, 88 <math>\mu</math>mol/L; ≥ 16 years, female 105.6 <math>\mu</math>mol/L, male 114.4 <math>\mu</math>mol/L.	N/A	Increase in the serum creatinine level of 0.3 mg/dL (26.5 $\mu$ mol/liter) or the presence of oliguria (average urine output of < 0.5 mL/kg/hr over a 6-hour period)

\* In laboratory tumor lysis syndrome ≥ 2 metabolic abnormalities must be present during the same 24-hour period within 3 days before the start of therapy or up to 7 afterwards.

\*\* Clinical TLS requires the presence of laboratory TLS plus an increased creatinine level, seizures, cardiac dysrhythmia, or death.

† Corrected calcium = measured calcium level in mg/dL + 0.8 x (4-albumin in g/dL).

‡ Acute kidney injury, unless attributable to another cause, represents clinical TLS even if criteria for laboratory TLS are not satisfied.

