### *Dose and Schedule:*

During Cycle 1, participants will take venetoclax 20 mg/day on Day 1, 50 mg/day on Day 2, 100 mg/day on Day 3, 200 mg/day on Day 4, 400 mg/day on Day 5, and 800 mg/day on Days 6-7 in the ramp-up phase and 800 mg/day on Days 8-28. Romidepsin 14 mg/m^2 will be administered on Days 1, 8, and 15 of the 28-day cycle.

During Cycle 2+, participants will take 800 mg/day venetoclax. Romidepsin 14 mg/m^2 will be administered on Days 1, 8, and 15 of each 28-day cycle.

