#### **5.2 Treatment Cycle Definition**

The treatment cycle will be a fixed 28 days (**Note:** exceptions due to unusual operational considerations may be permitted as described in [Section 6.2](#)).

[figure not shown]
The cycle day count and cycle count will continue despite a hold in venetoclax or romidepsin administration due to toxicities (See [Section 6.2](#)) - i.e. a cycle may initiate even if either drug is being held.

Cycle 1 Day 1 is defined as the first day of venetoclax and romidepsin administration.

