### 7.2 Treatment Modification Guidelines

Toxicity	Treatment Modification	
Metabolic and nutrition	Romidepsin	Venetoclax
Hyperuricemia, hyperphosphatemia, hyperkalemia, hypocalcemia and creatinine changes with no evidence of clinical TLS (See Appendix B ).  Potassium > 6.0 mmol/L  Potassium ≥ 0.5 mmol/L increase from prior value (even if potassium within normal limits [WNL])  Potassium > upper limit of normal Phosphorus > 4.5 mg/dL (1.5 mmol/L)  Uric acid > 8.0 mg/dL (475.8 µmol/L)		
 
• Hold the dose until resolution
 
• Refer to Section 5.10.3 for recommended supportive care.
 
• 1st occurrence 
 
– If resolved within 3 days to resume at the same dose
 
– If toxicity resolves > 3 days resume at a 50% dose reduction
 
 
 
• 2nd occurrence 
 
– If resolves within 3 days to ≤ Grade 1 or baseline,
 
 
 

Toxicity	Treatment Modification	
Metabolic and nutrition	Romidepsin	Venetoclax

Corrected calcium <7.0 mg/dL
 
Creatinine increase ≥ 25% from baseline
		
resume at a 50% dose reduction
 
 
– If toxicity lasts > 3 days permanently discontinue protocol therapy
 

Symptoms suggestive of clinical TLS (e.g. acute renal failure, cardiac arrhythmia, seizures) See Appendix B.
		
 
• Hold venetoclax dose until TLS is resolved
 
• If toxicity resolves within 24-48 hours resume venetoclax at current dose
 
• If toxicity takes longer than 48 hours to resolve, resume at the previous dose in the ramp sequence.2nd occurrence, consider permanently discontinuing protocol therapy
 

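### The laboratory-TLS window closes on Day 8, so after a Cycle 1 hold or reduction the highest venetoclax doses can fall outside the only TLS definition the protocol gives

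*Combined protocol and SAP*

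**What the plan says.** Appendix B, footnote *, requires two or more metabolic abnormalities for laboratory TLS, which "must be present during the same 24-hour period within 3 days before the start of therapy or up to 7 afterwards". The unit after 7 is missing; days are clearly meant. Footnote ** adds: "Clinical TLS requires the presence of laboratory TLS plus an increased creatinine level, seizures, cardiac dysrhythmia, or death". Footnote ‡ makes an exception for acute kidney injury, which, unless it has another cause, "represents clinical TLS even if criteria for laboratory TLS are not satisfied".

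The dosing clock is set in Section 5.2: "Cycle 1 Day 1 is defined as the first day of venetoclax and romidepsin administration", and "The cycle day count and cycle count will continue despite a hold in venetoclax or romidepsin administration due to toxicities". Section 2.7 (Dose and Schedule) raises venetoclax daily from 20 mg on Day 1 to 400 mg on Day 5, then "800 mg/day on Days 6-7 in the ramp-up phase and 800 mg/day on Days 8-28".

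Section 7.2 holds venetoclax for a single chemistry change without clinical TLS. At a first occurrence the instruction is "If resolved within 3 days to resume at the same dose"; if resolution takes longer, dosing resumes at half the dose. Section 7.1 allows daily re-escalation after a Cycle 1 reduction, following consultation with the Study PI. It ends treatment only if dosing cannot resume within 14 days of the last venetoclax dose.

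Dedicated TLS chemistry (Section 10.0, note w) is drawn before each of the Day 1 to Day 8 doses, and 6-8 h and 24 (±2) h after them. Table 5.9.1 is narrower: under a Day 1-8 heading, it ties the post-dose draws to dose increases.

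Section 12.4.1 suspends accrual at the first reported clinical TLS. Section 12.4.2 suspends it at 1 laboratory TLS in up to 5 patients, 2 in up to 14, or 3 at any time. Section 11.2 counts clinical TLS in the first two cycles as unacceptable toxicity in the lead-in.

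**The concern.** The window is fixed to the calendar, while the exposure that drives TLS follows the dosing. Section 2.3.2 itself says that TLS risk in CLL is highest while venetoclax is being titrated. Once a hold or reduction delays the ramp, the steps to the highest doses can fall after the window has closed.

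The patients affected are not a random subset. Several hold thresholds in Section 7.2 (uric acid, phosphorus, potassium above 6.0 mmol/L, corrected calcium) are the same as those in Appendix B. A patient held on one of them is one abnormality short of laboratory TLS.

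At stake is whether an event is counted. One laboratory TLS among the first 5 patients, or one clinical TLS at any time, suspends accrual and starts review by the protocol team and the DSMC. A single uncounted event can therefore decide whether the trial pauses.

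**Working it through.** **1. Where the window ends.** Start of therapy = Day 1 (5.2). Day 1 + 7 days = Day 8. Counted as exactly 168 hours, it closes on Day 8 at the clock time of the first dose.

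**2. No hold.** The last increase is to 800 mg on Day 6, and its 24 h sample is on Day 7, inside the window. Every earlier step is inside too. Under note w the Day 8 dose has a sample 22 to 26 h later, on Day 9, outside the window. Under Table 5.9.1 the last required post-dose sample would be the one on Day 7. The on-schedule gap is therefore one sample, and it rests on note w. That sample is also the only dedicated next-day TLS sample after the second romidepsin infusion, if that is given on Day 8.

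**3. After a hold.** The protocol does not say whether the ramp then resumes in sequence or by calendar day, so both readings are shown.

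| Reading | Hold | First 800 mg | 24 h after it |
|---|---|---|---|
| Sequential (Day 6 + h) | h = 1 day | Day 7 | Day 8, inside |
| Sequential | h = 2 days | Day 8 | Day 9, outside |
| Sequential | h = 3 days | Day 9 | Day 10, outside, no TLS draw scheduled |
| Calendar, missed doses skipped | Days 2-4 | Day 6 | Day 7, inside |
| Calendar, missed doses skipped | Days 6-8 | Day 9 | Day 10, outside, no TLS draw scheduled |

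Under either reading the 14-day limit leaves room for later dates. If the last dose was on Day 5, treatment may resume as late as Day 5 + 14 = Day 19. A dose reduction followed by re-escalation can also put increases after Day 8.

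**4. From the window to the rules.** Sections 12.4.1 and 12.4.2 contain no definition of TLS. Note d of Section 10.0 takes laboratory TLS from Appendix B. Section 11.2 cites the published criteria on which Appendix B is based. No other definition is given. Read literally, chemistry that first qualifies after Day 8 is not laboratory TLS for 12.4.2. By footnote **, a seizure, dysrhythmia or death with that chemistry is then not clinical TLS for 12.4.1 or 11.2. Kidney injury under ‡ still is. A patient who met laboratory TLS by Day 8 is already counted.

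**5. Illustration of size.** The plan's own figure first: 12.4.2 states a trigger probability below 50% at a true rate of 12% or less. At 12%, 1 − 0.88^5 = 47.2% for the first boundary, which agrees. But 2 or more of 14 gives 51.4%, and the whole rule applied after each of 20 patients (the maximum for the combination, 12.2) gives 66.4%. That is a separate matter, but it bears on the cost of the fix.

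Suppose a share f of patients with laboratory TLS first qualify after Day 8 and go uncounted. The counted rate is then p(1 − f), and the chance of suspension within 5 patients is 1 − (1 − p(1 − f))^5. For 20 patients the three boundaries are applied after each patient by exact binomial recursion. Both f and the true rate p are assumptions; the documents give neither.

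| True rate p | Patients | f = 0 | f = 10% | f = 25% | f = 50% |
|---|---|---|---|---|---|
| 12% | 5 | 47.2% | 43.5% | 37.6% | 26.6% |
| 20% | 5 | 67.2% | 62.9% | 55.6% | 41.0% |
| 30% | 5 | 83.2% | 79.3% | 72.0% | 55.6% |
| 12% | 20 | 66.4% | 61.1% | 52.1% | 35.1% |
| 20% | 20 | 89.6% | 85.6% | 77.5% | 57.2% |
| 30% | 20 | 98.4% | 97.0% | 93.2% | 77.5% |

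**The case against.** The strongest reply is that the window fits the planned ramp and that a late event would still be acted on. Much of this stands.

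- With no hold, all dose steps and their 24 h samples are inside the window, which covers the same Days 1-8 as the close monitoring in Section 5.5.
- A reader might infer that every held day pushes 800 mg back by one day. The documents do not support this. Withheld doses are not made up, Section 2.7 assigns doses to calendar days, and an early hold need not move 800 mg at all.
- A reader might infer that patients go unmonitored after Day 8. They do not. The panel in note v covers all five TLS analytes and is scheduled on Days 15 and 22 and weekly in Cycle 2. Extra tests are allowed, and Section 5.9.3 sets rechecks after abnormal values. What ends is the dedicated 6-8 h and 24 h sampling.
- A reader might infer that a late event would certainly go uncounted. Section 12.4.1 acts on clinical TLS that is reported, the investigator names the event (14.2), and any TLS needs an expedited report (14.5). A late event named as TLS could suspend accrual. Some events would also count in the lead-in under the other lines of 11.2, such as Grade 4 metabolic abnormalities not resolved within 3 days.

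What remains is that the protocol does not say whether the Appendix B window binds the person naming the event. A suspension rule should not depend on that choice. Reporting under 14.5 and the other lines of 11.2 do not by themselves trigger 12.4.

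**Conclusion.** The gap is real but conditional. It concerns the Day 9 sample in note w and, more importantly, patients whose venetoclax is held or reduced in Cycle 1 so that the first 800 mg dose or a re-escalation comes after Day 8. For them, a literal reading leaves TLS that first qualifies late outside 12.4.2 and, kidney injury apart, outside clinical TLS for 12.4.1 and 11.2.

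This rests on Appendix B being the operative definition and on the window being applied as written. Exclusion is a possible outcome, not a certain one. The documents give no frequency of holds or of late TLS, so the table shows only the direction and possible range of the effect. It would be wrong to read its lower entries as the trial's expected loss of protection: a late share of 50% is hard to square with a ramp that normally ends on Day 6, and 20% and 30% lie above the 12% benchmark. The response endpoint, the sample size and the error rates of the two-stage design are unaffected. It is worth correcting because one event can decide a pause and the correction is cheap.

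**What to change.** By amendment:

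- For 12.4 and 11.2, let the footnote * window run until 7 days after the last Cycle 1 venetoclax increase, including any re-escalation. With no hold this is Day 6 + 7 = Day 13, which takes in the Day 9 sample. It works whichever way the ramp resumes. The exact length is a clinical judgement for the sponsor.
- In Table 5.9.1 and note w, require the 6-8 h and 24 h TLS chemistry after every venetoclax increase, including those after Day 8.
- Add to footnote ** that it applies except as in ‡, and put no window on ‡.
- Report laboratory TLS by both the present 7-day window and the extended one, and state which window the 12% benchmark used.

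The cost is a few sentences and two blood draws per late increase, with no extra patients. The downside is that more events can count. If the 12% benchmark used the 7-day window, which the documents do not say, accrual may pause somewhat more often, under a rule that already triggers with 66.4% probability over 20 patients at a true rate of 12%. Reporting both windows keeps the benchmark comparison possible.

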**APPENDIX C-1: PTCL-DISEASE PARAMETERS & METHODS OF EVALUATION AND RESPONSE**

---

Response will be assessed per Lugano Classification [50]

**Disease Parameters**

- Measurable disease

Measurable lesions are defined as those that can be accurately measured in at least one dimension (longest diameter to be recorded) as  $\geq 15$  mm ( $\geq 1.5$  cm) by chest x-ray, CT scan, MRI, or calipers by clinical exam. All tumor measurements must be recorded in millimeters (or decimal fractions of centimeters).

Note: Tumor lesions that are situated in a previously irradiated area might or might not be considered measurable

- Malignant lymph nodes

To be considered pathologically enlarged and measurable, a lymph node must be  $\geq 15$  mm ( $\geq 1.5$  cm) in short axis when assessed by CT scan (CT scan slice thickness recommended to be no greater than 5 mm [0.5 cm]). At baseline and in follow-up, only the short axis will be measured and followed.

- Non-measurable disease

Pathological lymph nodes with  $\geq 10$  to  $<15$  mm [ $\geq 1$  to  $<1.5$  cm] short axis), are considered non-measurable disease. Bone lesions, leptomeningeal disease, ascites, pleural/pericardial effusions, lymphangitis cutis/pulmonitis, inflammatory breast disease, and abdominal masses (not followed by CT or MRI), are considered as non-measurable.

- Note: Cystic lesions that meet the criteria for radiographically defined simple cysts should not be considered as malignant lesions (neither measurable nor non-measurable) since they are, by definition, simple cysts.

- 'Cystic lesions' thought to represent cystic metastases can be considered as measurable lesions, if they meet the definition of measurability described above. However, if non-cystic lesions are present in the same patient, these are preferred for selection as target lesions.

- Target lesions

All measurable lesions up to a maximum of 2 lesions per organ and 5 lesions in total, representative of all involved organs, should be identified as target lesions and recorded and measured at baseline. Target lesions should be selected on the basis of their size (lesions with the longest diameter), be representative of all involved organs, but in addition should be those that lend themselves to reproducible repeated measurements. It may be the case that, on occasion, the largest lesion does not lend itself to reproducible measurement in which circumstance the next largest lesion which can be measured reproducibly should be selected. A sum of the diameters (longest for non-nodal lesions, short axis for nodal lesions) for all target lesions will be calculated and reported as the baseline sum diameters. If lymph nodes are to be included in the sum, then only the short axis is added into the sum. The baseline sum diameters will be used as reference to further characterize any objective tumor regression in the measurable dimension of the disease.

- Non-target lesions

All other lesions (or sites of disease) including any measurable lesions over and above the 5 target lesions should be identified as non-target lesions and should also be recorded at baseline. Measurements of these lesions are not required, but the presence, absence, or in rare cases unequivocal progression of each should be noted throughout follow-up.

### **Methods for Evaluation of Measurable Disease**

All measurements should be taken and recorded in metric notation using a ruler or calipers. All baseline evaluations should be performed as closely as possible to the beginning of treatment and never more than 4 weeks before the beginning of the treatment.

The same method of assessment and the same technique should be used to characterize each identified and reported lesion at baseline and during follow-up. Imaging-based evaluation is preferred to evaluation by clinical examination unless the lesion(s) being followed cannot be imaged but are assessable by clinical exam.

- Clinical lesions

Clinical lesions will only be considered measurable when they are superficial (e.g., skin nodules and palpable lymph nodes) and  $\geq 10$  mm ( $\geq 1$  cm) diameter as assessed using calipers (e.g., skin nodules). In the case of skin lesions, documentation by color photography, including a ruler to estimate the size of the lesion, is recommended.

- Conventional CT and MRI

This guideline has defined measurability of lesions on CT scan based on the assumption that CT slice thickness is 5 mm (0.5 cm) or less. If CT scans have slice thickness greater than 5 mm (0.5 cm), the minimum size for a measurable lesion should be twice the slice thickness. MRI is also acceptable in certain situations (e.g. for body scans).

Use of MRI remains a complex issue. MRI has excellent contrast, spatial, and temporal resolution; however, there are many image acquisition variables involved in MRI, which greatly impact image quality, lesion conspicuity, and measurement. Furthermore, the availability of MRI is variable globally. As with CT, if an MRI is performed, the technical specifications of the scanning sequences used should be optimized for the evaluation of the type and site of disease. Furthermore, as with CT, the modality used at follow-up should be the same as was used at baseline and the lesions should be measured/assessed on the same pulse sequence. It is beyond the scope of the Lugano Classification [5] to prescribe specific MRI pulse sequence parameters for all scanners, body parts, and diseases. For this trial, MRI will not be used as standard imaging study for disease assessment.

- **PET-CT** at present, the low dose or attenuation correction CT portion of a combined PET-CT is not always of optimal diagnostic CT quality for use with Lugano Classification [5]. However, if the site can document that the CT performed as part of a PET-CT is of identical diagnostic quality to a diagnostic CT (with IV and oral contrast), then the CT portion of the PET-CT can be used for measurements and can be used interchangeably with conventional CT in accurately measuring cancer lesions over time. Note, however, that the PET portion of the CT introduces additional data which may bias an investigator if it is not routinely or serially performed.

- **FDG-PET:** While FDG-PET response assessments need additional study, it is sometimes reasonable to incorporate the use of FDG-PET scanning to complement CT scanning in assessment of progression (particularly possible 'new' disease). New lesions on the basis of FDG-PET imaging can be identified according to the following algorithm:
  - Negative FDG-PET at baseline, with a positive FDG-PET at follow-up is a sign of PD based on a new lesion.
  - No FDG-PET at baseline and a positive FDG-PET at follow-up: If the positive FDG-PET at follow-up corresponds to a new site of disease confirmed by CT, this is PD. If the positive FDG-PET at follow-up is not confirmed as a new site of disease on CT, additional follow-up CT scans are needed to determine if there is truly progression occurring at that site (if so, the date of PD will be the date of the initial abnormal FDG-PET scan). If the positive FDG-PET at follow-up corresponds to a pre-existing site of disease on CT that is not progressing on the basis of the anatomic images, this is not PD.
  - FDG-PET may be used to upgrade a response to a CR in a manner similar to a biopsy in cases where a residual radiographic abnormality is thought to represent fibrosis or scarring. The use of FDG-PET in this circumstance should be prospectively described in the protocol and supported by disease-specific medical literature for the indication. However, it must be acknowledged that both approaches may lead to false positive CR due to limitations of FDG-PET and biopsy resolution/sensitivity.

**Note:** A 'positive' FDG-PET scan lesion means one which is FDG avid with an uptake greater than twice that of the surrounding tissue on the attenuation corrected image.

